**Table 4 Censoring rules for PFS**

Assessment	Outcome	Date of progression or censoring
Death before first response evaluation 	Event	Date of death
Documented PD between scheduled visits  (or, between a scheduled and unscheduled visit, if the unscheduled visit falls in between two scheduled visits) on or before receiving subsequent anti-cancer therapy or data cutoff, whichever occurred first	Event	Earliest date of disease assessment documenting progression
Death without documented PD  and not receiving subsequent anti-cancer therapy on or before data cutoff	Event	Date of death
No baseline tumor assessments and it's not known to have died in 2 consecutive visits of baseline. In cases of no measurable disease at baseline censoring will not occur.	Censored	Date of randomization
No adequate post-baseline response evaluations and is not known to have died in 2 consecutive visits of baseline	Censored	Date of randomization
Documented PD or death after subsequent anti-cancer therapy and the subsequent anti-cancer started before data cutoff date	Censored	Date of last adequate disease assessment prior to subsequent anti-cancer treatment
No documented PD or death at the time of data cutoff and subsequent anti-cancer therapy started before the data cutoff	Censored	Date of last adequate disease assessment prior to subsequent anti-cancer treatment
Documented PD or death after subsequent anticancer therapy and the subsequent anticancer started after data cutoff date	Censored	Date of last adequate disease assessment on or before data cutoff
No documented PD or death at the time of data cutoff and patient not received subsequent anticancer therapy or subsequent anticancer therapy started after the data cutoff	Censored	Date of last adequate disease assessment on or before data cutoff
Withdrew consent without documented PD or death	Censored	Date of last adequate disease assessment on or before date of withdrawn consent
Lost to follow-up without documented PD or death	Censored	Date of last adequate disease assessment on or before data cutoff
Documented PD or death after 2 or more consecutively missed response evaluations	Censored	Date of last adequate disease assessment before the consecutively missed visits

 Having not missed 2 consecutive response evaluations.

Note: Because several assessments contribute to response evaluation for all the scenarios described above the date of 'disease assessment' means the date of the last assessment contributing to the response evaluation.

PD = progressive disease.

An adequate disease assessment is defined by a BICR IWCLL 2018 response that is not 'UNK' (unknown) or missing.

The following rules will be used to determine if a patient has missed two consecutive response evaluations:

CCI

CCI

For the purposes of calculating the time between assessments a response evaluation of UNK would not be considered missing.

PFS will also be obtained using the same derivation rule described above but based on investigator assessment.

### 3.3.2 Overall response rate (ORR)

ORR is defined as the proportion of patients who have a best overall response of CR, CRi, nPR or PR assessed by BICR per IWCLL 2018 criteria at or before initiation of subsequent anti-cancer therapy. CRi refers to patients who fulfil all the criteria for a CR (including the bone marrow examinations), but have a persistent anemia, thrombocytopenia, or neutropenia apparently unrelated to CLL, but related to drug toxicity. nPR refers to patients who fulfil all the criteria for a CR but with the presence of B-lymphoid nodules in the bone marrow which reflect residual disease. See [Section 3.3.3](#) for more information on how best overall response is determined.

As per the study inclusion criteria all patients enrolled onto the study should have active disease per IWCLL 2018 criteria. Therefore, the FAS will be used as the denominator for calculating ORR. For subjects with CLL who achieve a response (CR, CRi, nPR, PR), CT must be performed for response confirmation after 8 weeks (>56 days) after the initial response imaging assessment.

ORR plus patients with a best overall response of PRL will also be assessed, denoted as ORR+PRL.

ORR and ORR+PRL will also be obtained using the same derivation rule described above based on investigator assessment.

### 3.3.3 Best overall response (BOR)

Best overall response is the best response a patient has had following randomization, but prior to starting any subsequent anticancer therapy up to and including progression or the last evaluable assessment in the absence of progression. To determine the BOR, the following order is used: CR > CRi > nPR > PR > PRL > SD > PD > UNK.

Patients will be assigned a BOR of UNK (Unknown) if all post-baseline responses are either missing (not documented) or documented as NA (Not Applicable) or Unknown.

BOR will also be obtained using the same derivation rule described above based on investigator assessment.

The overall response concordance rate will be calculated as the proportion of patients in the FAS who have the same CR+CRi+nPR+PR according to the BICR and the investigator. The concordance rate of CR+CRi will be calculated similarly.

### **3.3.4 Duration of response (DoR)**

DoR (assessed by BICR per IWCLL 2018 criteria) is defined as the time from the date of first documented response until date of documented progression or death in the absence of disease progression (i.e. date of PFS event or censoring – date of first response + 1). DoR will therefore only be calculated for patients with overall response, as documented in [Section 3.3.2](#). Date of response will be defined as the date of the last assessment contributing to the response evaluation where an overall response is first recorded. DoR will use the same event and censoring rules as PFS (see [Section 3.3.1](#) for further details).

DoR will also be obtained using the same derivation rule described above based on investigator assessment.

### **3.3.5 Time to next therapy (TTNT)**

TTNT is defined as the time from the date of randomization until institution of non-protocol specified treatment for CLL (either medication or radiotherapy for CLL) or death due to any cause, whichever comes first (i.e. date of first subsequent cancer therapy/death or censoring – date of randomization + 1). Any patient not known to have had a first subsequent anti-cancer therapy will be censored at the last date that the patient was known not to have received a first subsequent anti-cancer therapy (obtained from the CAPRX1 and CAPRXRCL1 forms). If the follow-up cancer therapy eCRF has not been completed then the last known alive date will be used for censoring, considering the following eCRFs:

- AE start and stop dates
- Admission and discharge dates of hospitalization
- Study treatment date
- End of treatment date
- Laboratory sample dates
- Date of vital signs
- Date of ECGs

- Concomitant medications start and stop dates
- Disease assessment dates on IWCLL 2018 eCRF
- Start and stop dates of alternative anti-cancer treatment
- Date last known alive on survival status eCRF
- End of study date.

Patients who are ongoing randomized treatment will be censored at the date of last study visit, using the same criteria defined above. If a patient terminated the study for reason other than death without subsequent therapy, these patients will be censored at the earliest of their last known to be alive and termination dates. For the Interim Analysis, DCO date will be used.

Subsequent anticancer therapies are defined as medications/radiation therapies that:

- Had an indication for the primary malignancy CLL,
- Had start date after study treatment completion or discontinuation.

The start date of subsequent anticancer therapy is defined as the first dose date of the subsequent anticancer therapy.

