9.4.1.4 Time to next therapy

Time to next therapy (TTNT) is defined as time from randomization until institution of non-protocol specified treatment for CLL or death due to any cause, whichever comes first. As for the detailed censoring rules, please refer to the statistical analysis plan (SAP).

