### 1.1 Study Objectives

**Table 1 Study Objectives**

Primary objective:	Endpoint/variable
To compare the efficacy of acalabrutinib relative to chlorambucil plus rituximab in subjects with previously untreated chronic lymphocytic leukemia without del(17p) or TP53 mutation.	Progression free survival is defined as time from randomization until progression per the International Workshop on Chronic Lymphocytic Leukemia 2018 criteria as assessed by blinded independent central review or death due to any cause.
Secondary objectives:	Endpoints/variables:
To compare acalabrutinib relative to chlorambucil plus rituximab on objective response rate, duration of response, time to next treatment, and overall survival.	
 
• Overall response rate is defined as the proportion of patients who have a complete response, complete response with incomplete bone marrow recovery, nodular partial response or partial response, as determined by blinded independent central review and investigator per International Workshop on Chronic Lymphocytic Leukemia 2018 criteria.
 
• Duration of response is defined as the time from the date of first documented response until date of documented progression or death in the absence of disease progression, as determined by blinded independent central review and investigator.
 
• Time to next therapy is defined as time from randomization until institution of non-protocol specified treatment for chronic lymphocytic leukemia.
 
• Overall survival is the length of time from randomization until the date of death due to any cause.
 

To evaluate minimal residual disease negativity rate during treatment and at the end of treatment.	Minimal residual disease negativity rate (peripheral blood) at the start of Cycle 9.

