## 2. ANALYSIS SETS

### 2.1 Definition of Analysis Sets

#### **Full analysis set (FAS)**

Includes all randomized patients. Patients will be analyzed by treatment group assigned in accordance with the randomization, regardless of the treatment actually received. Patients who were randomized but did not subsequently receive treatment are included in the FAS. The analysis of data using the FAS therefore follows the principles of intent to treat (ITT).

Unless otherwise specified, all analyses using the FAS will include data only prior to crossover for patients from Arm B. Overall FAS is defined as all randomized patients in the study.

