### **3. PRIMARY AND SECONDARY VARIABLES**

#### **3.1 Handling of crossover patients**

Patients in Arm B who have BICR-confirmed progression will have the option to crossover to acalabrutinib. For all efficacy analyses, except for the analysis of OS, will include data prior to crossover. OS will encompass the entire study duration.

All safety analyses, except that for death, will include data prior to crossover unless noted otherwise. Death will be summarized in the following three ways: over the randomized period, crossover period and entire study duration.

The crossover period is defined only for patients who were randomized and received at least one dose of crossover therapy.

Prior to crossover first/last dose refers to the first/last dose of chlorambucil/rituximab. Post crossover first/last dose refers to the first/last dose of acalabrutinib.

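### The SAP's time-to-next-therapy rules conflict on whether Arm B crossover to acalabrutinib is an event or a censoring point, and nothing in the plan reconciles them

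*SAP*

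**What the plan says.** **Text that leads to censoring.** SAP 3.3.5 opens with "TTNT is defined as the time from the date of randomization until institution of non-protocol specified treatment for CLL", or death if earlier. Protocol 9.4.1.4 has the same event, "time from randomization until institution of non-protocol specified treatment for CLL or death due to any cause, whichever comes first", and leaves the detailed censoring rules to the SAP. The objectives tables in both documents carry the same restriction to treatment outside the protocol; SAP Table 1 reads "Time to next therapy is defined as time from randomization until institution of non-protocol specified treatment for chronic lymphocytic leukemia". On data after crossover, SAP 3.1 states: "For all efficacy analyses, except for the analysis of OS, will include data prior to crossover". SAP 2.1 adds: "Unless otherwise specified, all analyses using the FAS will include data only prior to crossover for patients from Arm B". Neither SAP 3.3.5 nor SAP 4.2.2.6, the TTNT analysis section, mentions crossover.

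**Text that leads to an event.** The same sentence of SAP 3.3.5 gives the computed quantity as "date of first subsequent cancer therapy/death or censoring" minus randomization plus one day. The section ends by defining subsequent therapies with two conditions: an indication for CLL, and "Had start date after study treatment completion or discontinuation". For Arm B, SAP 3.1 says "Prior to crossover first/last dose refers to the first/last dose of chlorambucil/rituximab", so crossover acalabrutinib starts after that treatment. SAP 3.5.2, 4.2.6.3, 4.2.6.4 and 4.2.6.5 name crossover as one of the subsequent therapies that close the safety windows. SAP 4.2.6.2 flags events after crossover and then events after any other subsequent therapy.

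**Crossover itself.** Protocol 6.8 offers acalabrutinib to Arm B patients after confirmed progression and bars any other CLL therapy between Arm B treatment and crossover.

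**The concern.** TTNT is a named secondary endpoint with a stratified log-rank test (SAP Table 7) and a stratified Cox hazard ratio (SAP 4.2.2.1). Two competent programmers could follow this SAP and give crossover patients opposite status.

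The two choices are not equally harmless. For a patient who crosses over, crossover is the next CLL therapy, because Protocol 6.8 rules out anything in between. Censoring there removes the very outcome that TTNT measures. It does so because the patient has progressed, and in one arm only, since Arm A has no crossover and its next therapies all count. Any death after crossover would drop out of TTNT too. SAP Table 7 plans a crossover sensitivity analysis for OS and none for TTNT, so the planned outputs would not show which rule was used or how much it mattered.

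**Working it through.** **Step 1: follow each route through the text for one Arm B patient who progresses and crosses over.**

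| Rule | Applied to the first crossover dose |
|---|---|
| SAP 3.3.5, definition sentence; Protocol 9.4.1.4 | Provided by Protocol 6.8, so not treatment outside the protocol: no event |
| SAP 3.1 and 2.1, data cut | TTNT is not exempted; later data are dropped |
| SAP 3.3.5, general censoring rule | Censored at the last date known free of subsequent therapy, at or shortly before the first crossover dose |
| SAP 3.3.5, closing definition, with the dose rule in SAP 3.1 | CLL indication met; start after chlorambucil/rituximab met: event |

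The data cut alone does not force censoring, because the first crossover dose sits on the boundary. The cut combined with the definition sentence does.

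**Step 2: check the inputs to be reused.** The documents give no TTNT figure, so the PFS design is the only check available. With 50 events and HR 0.333, power is Φ(|ln 0.333|·√50/2 − 1.96) = Φ(3.888 − 1.960) = 97.3%. With the interim at 38 events it is 97.1%. Nominal levels come to 0.0203 and 0.0440. The plan states more than 95%, 0.02 and 0.044, so the inputs reproduce.

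**Step 3: illustrate the size.** From the documents: 75 per arm, 30-month accrual, median PFS 30 and 90 months, analysis at about 45 months (Protocol 4.4). Monthly hazards are hB = ln 2/30 = 0.0231 and hA = ln 2/90 = 0.0077. Assumed, because the documents are silent: a death hazard d = 0.002 per month inside each PFS hazard, and every progressor starting next therapy 2 months after progression. Let x be the share of Arm B **progressors** who cross over. Ignoring the lag, censoring them gives

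HR = hA / (hB − x(hB − d)).

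- x = 0: 0.0077/0.0231 = 0.33
- x = 10%: 0.0077/0.0210 = 0.37
- x = 30%: 0.0077/0.0168 = 0.46
- x = 50%: 0.0077/0.0126 = 0.61
- HR = 1 at x = (hB − hA)/(hB − d) = 0.0154/0.0211 = 73% (70% to 81% for d from 0.001 to 0.004)

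Simulation with the 2-month lag (2,000 trials per scenario, unstratified):

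| Rule | Median HR | Arm B events | Arm B patients censored at crossover | Chance of nominal p<0.05 for acalabrutinib |
|---|---|---|---|---|
| Crossover counted | 0.34 | 35.1 | 0 | 97% |
| Censored, x = 10% | 0.37 | 31.9 | 3.2 | 91% |
| Censored, x = 30% | 0.46 | 25.7 | 9.4 | 66% |
| Censored, x = 50% | 0.62 | 19.3 | 15.8 | 29% |

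The denominator matters: x = 50% corresponds to 15.8/75 = 21% of Arm B patients crossing over by the cut-off. If the share is expressed instead as q, the share of Arm B first TTNT events that are crossover starts, then HR = 0.333/(1 − q), which is 0.44 at q = 25%, 0.67 at 50% and 1 at 67%. The two forms agree, since q = x(hB − d)/hB = 0.913x.

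**Step 4: vary the assumptions.** Death hazards of 0.001 to 0.004 and lags of 0 to 6 months keep the censored HR at 0.45 to 0.48 for x = 30% and 0.58 to 0.65 for x = 50%. If only 85%, 70% or 50% of progressors start any next therapy, the HR with crossover counted is 0.36, 0.39 or 0.44. With crossover censored it is 0.50, 0.53 or 0.58 when 30% of those treated progressors cross over, and 0.65, 0.69 or 0.74 when 50% do. The model predicts about 52 PFS events at 45 months without dropout; Protocol 1.2 reports 48 at the cut-off.

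**The case against.** The strongest reply is that SAP 3.3.5 supplies its own working rule. The formula in its first sentence uses the first subsequent cancer therapy, the closing bullets define that term, and crossover meets both. The SAP amendment history records that further definitions of subsequent therapies were added to this section in version 2.0. The restriction to treatment outside the protocol is, by contrast, general wording shared with the objectives tables. Wherever the SAP mentions crossover and subsequent therapy together, it treats the first as a case of the second. The limit in SAP 2.1 yields where something else is specified, and the definition in 3.3.5 can be read as doing so. If crossover is an event, no TTNT crossover sensitivity analysis is needed.

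Most of this stands, and it makes the event reading the likelier intention. It does not close the point. The explicit mention of crossover appears in the safety sections and is absent from 3.3.5. SAP 3.1 exempts OS by name and nothing else. Protocol 6 includes acalabrutinib in its definition of study treatment, which leaves the bullet on treatment completion open to argument.

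A reader might infer that crossover patients were in fact censored, or that SAP 3.3.5 as a whole counts only therapy outside the protocol. The documents support neither: the first is not recorded, and the second is true of the definition sentence but not of the section.

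**Conclusion.** This is an unreconciled conflict in the definition of a tested secondary endpoint and should be fixed. Confidence is high that the texts conflict; which rule was programmed is unknown.

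Under the censoring reading the direction is clear: Arm B loses events, Arm A does not, and the hazard ratio moves towards or past 1, against acalabrutinib. The size cannot be stated. The shift from 0.34 to 0.37, 0.46 or 0.62 rests on an assumed crossover share among progressors, an assumed death hazard and, in the base case, next therapy for every progressor.

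Two further inferences should be resisted. The percentages are not shares of all Arm B patients, and the documents give no basis for expecting crossover high enough to bring the ratio to 1. Nor does the point touch the trial's main conclusion: up to the final analysis crossover required BICR-confirmed progression, so it followed the PFS event; SAP 4.2.1 allocates alpha to PFS only; and SAP 4.1 ties study success to PFS.

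**What to change.** Protocol 1.2 says the study was unblinded after the 3 January 2024 cut-off, so the order matters.

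1. State in the CSR which TTNT rule was programmed for that cut-off.
2. Reconcile SAP 3.3.5 with SAP 3.1 and 2.1, Protocol 9.4.1.4 and the objectives tables: the first dose of crossover acalabrutinib counts as next anti-CLL therapy, and TTNT is exempt from the pre-crossover cut for that date.
3. Report the other rule as a sensitivity analysis, with the number of Arm B patients who crossed over.
4. If crossover was censored in the programmed analysis, label the change as made after unblinding and do not present it as the pre-planned rule.

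The cost is one extra TTNT analysis and a short disclosure in the CSR. The crossover first-dose date is already needed for the OS sensitivity analysis in SAP 4.2.2.7, so no new data are required.

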Study ACE-CL-007 enrolled and randomized a total of 535 subjects (08 February 2019), and 526 subjects (98.3%) were treated with at least one study drug. The median time on study for acalabrutinib + obinutuzumab, acalabrutinib monotherapy, and obinutuzumab + chlorambucil subjects was 28.5 months (range: 1.7-40.3 months), 28.4 months (range: 0.1-40.8 months), and 28.0 months (range: 0.0-40.4 months), respectively. Acalabrutinib+obinutuzumab demonstrated a statistically significant improvement in BICR-assessed PFS compared with obinutuzumab+chlorambucil, with a 90% reduction in risk of disease progression or death (HR=0.10 [95% CI: 0.06, 0.17]; p<0.0001). Acalabrutinib monotherapy also demonstrated a statistically significant improvement in BICR-assessed PFS compared with obinutuzumab + chlorambucil, with an 80% reduction in risk of disease progression or death (HR=0.20 [95% CI: 0.13, 0.30]; p<0.0001). The median estimated PFS was not reached for acalabrutinib + obinutuzumab or acalabrutinib monotherapy and was 22.6 months (95%CI: 20.2, 27.6) for obinutuzumab + chlorambucil. The KM estimated 24-month PFS rate for acalabrutinib + obinutuzumab was 92.7% (CI 95%: 87.4, 95.8), acalabrutinib monotherapy was 87.3% (CI 95%: 80.9, 91.7), and obinutuzumab + chlorambucil was 46.7% (CI 95%: 38.5, 54.6).

The key sensitivity analysis of PFS without censoring for subsequent anticancer therapy was consistent with the primary analysis and showed similar improvement in PFS for acalabrutinib + obinutuzumab and acalabrutinib monotherapy compared with obinutuzumab+chlorambucil (HR=0.11 [95% CI: 0.06, 0.18] and HR=0.20 [95% CI: 0.13, 0.31], respectively). All other sensitivity analyses were also consistent with the primary analysis. The clinical benefit with acalabrutinib was further demonstrated by a significant prolongation of TTNT compared with obinutuzumab+chlorambucil for both acalabrutinib + obinutuzumab (HR=0.14 [95% CI: 0.08, 0.26]; p<0.0001) and acalabrutinib monotherapy (HR=0.24 [95% CI: 0.15, 0.40]; p<0.0001). BICR-assessed ORR for acalabrutinib + obinutuzumab and obinutuzumab+chlorambucil was 93.9% (95% CI: 89.3, 96.5) and 78.5% (95% CI: 71.9, 83.9), respectively, with a statistically significant difference between treatment arms of 15.3%p<0.0001). The BICR-assessed ORR in the acalabrutinib monotherapy arm was 85.5% (95% CI: 79.6, 89.9) (p=0.0763 compared with the obinutuzumab+chlorambucil arm).

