7.1 Discontinuation of study treatment

Subjects may be discontinued from IP in the following situations (note that discontinuation from study treatment is NOT the same thing as a complete withdrawal from the study):

- Any subject who has objective evidence of disease progression while receiving protocol required study drug should be discontinued from the study treatment. If there is uncertainty regarding whether there is disease progression, the subject may continue study treatment and remain under disease evaluation until confirmation of disease progression. In particular, transient worsening of disease during temporary interruption of study therapy (e.g., for drug-related toxicity, surgery, or intercurrent illness) may not indicate disease progression. In such circumstances, and if medically appropriate, subjects may resume therapy and relevant clinical, laboratory, and/or radiographic assessments should be done to document whether tumor control can be maintained or whether actual disease progression has occurred.
- Any AE that presents a substantial clinical risk to the subject with continued study treatment dosing.
- Subject decision. The subject is at any time free to discontinue treatment, without prejudice to further treatment.
- Pregnancy in a subject, intend to become pregnant or begin breast feeding.
- Severe non-compliance with the clinical study protocol.
- Start of alternative anti-CLL therapy.
- Study terminated by sponsor.

See the SoA for data to be collected at the time of treatment discontinuation and follow-up and for any further evaluations that need to be completed. Subjects that discontinue study treatment will continue with study follow-up visits until death, withdrawal of consent, lost to follow-up, or study termination, whichever occurs first.

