## 3.3 Efficacy Variables

### 3.3.1 Progression free survival (PFS)

PFS is defined as the time period from the date of randomization until progression or death from any cause, whichever occurs first (i.e. date of PFS event or censoring – date of randomization + 1, time period is calculated in months). Patients who withdraw from the study or are considered lost to follow-up without prior documentation of disease progression will be censored on the date of the last adequate disease assessment. However, if the patient progresses or dies immediately after two or more consecutive missed response evaluations, the patient will be censored at the time of the latest adequate disease assessment prior to the two or more missed visits. Patients who start new anti-cancer therapy before documentation of disease progression will be censored on the date of the last adequate disease assessment that is on or before the start date of the new anti-cancer therapy. For patients without an adequate post-baseline disease assessment or no baseline assessments, PFS will be censored on the date of randomization unless they die within 2 visits of baseline. Detailed censoring rules are described below.

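### SAP 3.3.5 counts a next CLL therapy only if it starts after study drug has ended, which is narrower than the TTNT endpoint and cannot be applied to untreated patients

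*SAP*

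**What the plan says.** SAP 3.3.5 opens with the endpoint: "TTNT is defined as the time from the date of randomization until institution of non-protocol specified treatment for CLL", or death if earlier. Nothing in that sentence depends on whether study drug has stopped. Protocol 9.4.1.4 gives the same definition and leaves only the detailed censoring rules to the SAP.

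The derivation in SAP 3.3.5 is "date of first subsequent cancer therapy/death or censoring – date of randomization + 1". The section closes by defining subsequent therapies through two conditions: "Had an indication for the primary malignancy CLL" and "Had start date after study treatment completion or discontinuation". It does not say whether discontinuation means the date of last dose or the date the decision was recorded. SAP Section 6, which lists changes from the protocol, does not mention the second condition.

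Three other provisions bear on it:

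- Protocol 7.1 lists "Start of alternative anti-CLL therapy" among the reasons for stopping study drug.
- SAP 2.1 states: "Patients who were randomized but did not subsequently receive treatment are included in the FAS". SAP Table 2 makes the FAS the analysis set for PFS, ORR, DoR and TTNT.
- For PFS, the text of SAP 3.3.1 reads: "Patients who start new anti-cancer therapy before documentation of disease progression will be censored on the date of the last adequate disease assessment". Protocol 9.4.1.1 also speaks of 'new' therapy. SAP Table 4 and SAP 3.3.2 and 3.3.3 say 'subsequent', and the only explicit definition of that word is the one in 3.3.5.

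**The concern.** The programmed TTNT event is narrower than the endpoint it should measure, and the cases that fall out are foreseeable. If starting another CLL drug is itself a reason to stop study drug, some patients will start it on or before the date recorded as discontinuation. A patient who never took study drug has no completion or discontinuation date, so the condition has nothing to be compared with.

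The first gap differs by arm. Acalabrutinib is given until progression or another stopping criterion, so the gap is open for Arm A's whole treatment period. Arm B is treated for at most 6 cycles of 28 days, or 168 days. TTNT is a secondary endpoint with a stratified log-rank test, so events lost or delayed mainly in one arm would matter. There is also a reproducibility problem: two programmers could derive PFS censoring differently, one following the text of 3.3.1 and the other Table 4 with the 3.3.5 definition.

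**Working it through.** **The plan's nearest figure.** No stated number rests on this rule. The nearest is PFS power above 95% (SAP 1.3: HR 0.333, 50 events, 1:1, two-sided 0.05). By the Schoenfeld formula, power = Φ(|ln HR|·√(D/4) − z). With |ln 0.333| = 1.0996 and √(50/4) = 3.536, the product is 3.888.

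- At alpha 0.05: Φ(3.888 − 1.960) = 0.973.
- At alpha 0.044: Φ(3.888 − 2.014) = 0.970.
- Group-sequential, with O'Brien-Fleming-type spending at 38/50: 0.971, with nominal levels 0.0203 and 0.0440 (SAP: 0.02 and 0.044).

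The stated figures reproduce.

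**The rule applied to cases.** Study days are illustrative. The test is start date later than discontinuation date, under both readings of discontinuation.

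| New CLL therapy starts | Last dose | Decision recorded | Counted if last dose is used | Counted if decision date is used | Event under the TTNT definition |
|---|---|---|---|---|---|
| Day 100 | Day 99 | Day 104 | Yes | No | Yes |
| Day 100 | Day 95 | Day 104 | Yes | No | Yes |
| Day 100 | Day 100 | Day 104 | No | No | Yes |
| Day 100 | Day 103 | Day 104 | No | No | Yes |
| Day 20 | Never treated | None | Cannot be evaluated | Cannot be evaluated | Yes |

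Same-day and overlapping starts fail on either reading. Starts between last dose and decision depend on the undefined date. SAP 3.5.1 (discontinuation during an interruption) and SAP 4.2.8 (post-treatment medication) use the last dose, but neither is tied to 3.3.5. A missed start is not always lost for good: a later regimen or death would still be an event, at a later date.

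**How many patients.** The documents give no count for this trial. For untreated patients, Protocol 2.2.3 describes two related trials:

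- In one, "526 subjects (98.3%) were treated with at least one study drug" out of 535 randomised: 535 − 526 = 9, and 9/535 = 1.7%. Applied here, 0.0168 × 150 = 2.5.
- In the other, 3 of 310 were untreated (1 acalabrutinib, 2 comparator): 3/310 = 1.0%, and 0.0097 × 150 = 1.5.

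Nothing in the documents anchors the number of same-day or overlapping starts.

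**Scale for PFS, by assumption.** If 1, 2, 4 or 8 of 150 patients were affected and each cost one PFS event, power at alpha 0.044 would be 0.967, 0.964, 0.957 or 0.939. This shows scale only. Failing to censor at new therapy would add events, so the effect could run the other way.

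**Direction for TTNT.** Losing or delaying Arm A events lowers the hazard ratio, in favour of acalabrutinib. If untreated patients are mainly controls who decline their open-label assignment (an assumption), the second gap loses Arm B events and pulls the ratio towards 1.

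**The case against.** The strongest reply is that the endpoint sentence in SAP 3.3.5 already counts any CLL therapy outside the protocol, that other sections date the end of treatment by last dose, and that other anticancer therapy during study drug is not allowed (Protocol 6.5.2, SAP 4.2.8). On that view few patients could be affected. TTNT also carries no allocated alpha, since success rests on PFS alone. Most of this stands as a limit on size. It does not remove the conflict, because the derivation uses the restricted term, and SAP 2.2 itself provides a deviation category for excluded medications.

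Four stronger readings are tempting, and the documents do not support them.

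- *Therapy that prompts discontinuation never counts.* It counts if it starts after the last dose and discontinuation is dated by last dose.
- *PFS runs through the new drug for all these patients.* The text of SAP 3.3.1 and Protocol 9.4.1.1 censor at 'new' therapy without the condition. Patients with no usable response assessment after baseline are censored at randomisation anyway, unless they die within two visits. SAP 4.2.2.2 also plans a PFS analysis without censoring at subsequent therapy.
- *TTNT is biased towards acalabrutinib.* That follows for the on-treatment gap alone; the untreated-patient gap may act in the opposite direction.
- *The hazard ratio shifts by 7% to 25%.* This comes from removing 1 or 2 of an assumed 8 to 15 Arm A events (1/15 = 7%, 2/8 = 25%). The only sourced counts are untreated patients across all arms, so they cannot size an Arm A loss. The sum also treats delayed events as lost.

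**Conclusion.** The conflict is real. The second condition in SAP 3.3.5 is narrower than the TTNT definition in the same section and in Protocol 9.4.1.4. Read literally, it omits or delays events for same-day and overlapping CLL therapy, leaves starts between last dose and recorded discontinuation to an undefined date, and does not cover untreated FAS patients. For PFS, ORR and BOR it is an unresolved ambiguity over which definition governs; DoR inherits it from PFS.

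The net direction of any TTNT bias is uncertain. The number affected is not given and is probably small: about 1.5 to 2.5 untreated patients if the related trials' rates carry over, plus an unknown number of same-day or overlapping starts. Not every untreated patient would go on to a countable therapy. No stated sample size, power or alpha is wrong on this account. The point deserves correction because the rule gives a wrong result in foreseeable cases and is cheap to repair.

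**What to change.** Replace the second condition in SAP 3.3.5 with: *started on or after randomisation and is CLL treatment not specified by the protocol, whether study treatment was never started, is ongoing or has stopped*. Apply it to every FAS patient. Use this one term in SAP 3.3.1, Table 4, 3.3.2, 3.3.3 and 3.3.5.

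Keep crossover acalabrutinib outside the definition and state its handling explicitly. It is specified in Protocol 6.8, and SAP 3.1 limits efficacy analyses other than OS to data before crossover. A looser phrase, such as any treatment other than the assigned one, would turn crossover into an Arm B TTNT event and change the endpoint. SAP 3.5.2 already includes crossover under subsequent therapy for the safety window, so silence would leave the word with two meanings.

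The Protocol synopsis records that the analysis at the 03 January 2024 cutoff, with 48 events, was taken as final and the study unblinded. The correction should therefore be transparent: list the affected patients, report TTNT under both definitions, and do the same for PFS if any patient's status or date changes.

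The cost is one SAP line, an indication check on a few on-treatment medications, and a small re-derivation. Because the PFS wording in Protocol 9.4.1.1 is not limited to CLL therapy, adopting the CLL-limited term there should be recorded in SAP Section 6 as a deliberate choice.
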